9.3 Pregnancy and Lactation Reporting

If a pregnancy occurs in a female subject, or female partner of a male subject, while the subject is taking protocol-required therapies, the pregnancy should be reported to Amgen as specified below.

In addition to reporting any pregnancies occurring during the study, investigators should monitor for pregnancies that occur after the last dose of protocol-required therapies and for an additional 15 weeks after the end of treatment with evolocumab.

The pregnancy should be reported to Amgen Global Patient Safety within 24 hours of the investigator's knowledge of the event of a pregnancy. The pregnancy should be reported on the Pregnancy Notification Worksheet ([Appendix C](#)). Amgen Global Patient Safety will follow up with the investigator regarding additional information that may be requested.

If a lactation case occurs while the female subject is taking protocol-required therapies, the lactation case should be reported to Amgen as specified below.

In addition to reporting a lactation case during the study, investigators should monitor for lactation cases that occur after the last dose of protocol-required therapies and for an additional 15 weeks after the end of treatment with evolocumab.

Any lactation case should be reported to Amgen Global Patient Safety within 24 hours of the investigator's knowledge of event. A lactation case should be reported on the Lactation Notification Worksheet ([Appendix C](#)). Amgen Global Patient Safety will follow up with the investigator regarding additional information that may be requested.

Amgen is sponsoring 2 prospective, observational studies of pregnant women who have been exposed to Repatha® (evolocumab) at any point during pregnancy and/or breastfeeding. One study registry is conducted in the US and Canada, and the other one in Europe, South Africa, and Australia. Participants are not asked to make any changes to their healthcare routine. While subjects who are pregnant are not eligible for the 20130295 study, if a site investigator/health care practitioner has a subject who becomes pregnant while receiving evolocumab, they will be advised to refer the subject

Approved

to Amgen's evolocumab pregnancy registry according to the place of residency. To learn more about the study in the US and Canada, you can go to MotherToBaby.org or call at [contact]. More information on the pregnancy registry study in Europe, South Africa, and Australia is available in the respective study protocol (Protocol ID: 20150162 and the following websites; ClinicalTrials.gov and AmgenTrials.com).

10. STATISTICAL CONSIDERATIONS

10.1 Study Endpoints, Analysis Sets, and Covariates

10.1.1 Study Endpoints

10.1.1.1 Primary Endpoint

The primary endpoint is the subject incidence of adverse events.

10.1.1.2 Secondary Endpoints

The secondary endpoints are the following:

- percent change of LDL-C from baseline at each scheduled visit
- achievement of an LDL-C < 40 mg/dL (1.03 mmol/L) at each scheduled visit

10.1.1.3 Exploratory Endpoints

The exploratory endpoints in subjects who completed the EBBINGHAUS study are the following:

- SWM strategy index of executive function
- SWM between-errors score
- PAL total errors adjusted
- RTI median 5-choice reaction time

The exploratory endpoints in all subjects are the following:

- change and percent change from baseline at each scheduled visit in each of the following lipid parameters:
 - total cholesterol
 - triglycerides
 - LDL-C
 - HDL-C
 - VLDL-C
 - non-HDL-C
 - ApoA1

Approved

- ApoB
- Lp(a)
- subject incidence of events positively reviewed by the CEC:
 - all deaths
 - cardiovascular events of interest:
 - MI
 - stroke
 - coronary revascularization
 - hospitalization for unstable angina
 - hospitalization for heart failure
 - TIA

10.1.2 Analysis Sets

The long-term safety analysis set (FOURIER and OLE studies) includes all subjects who were randomized to and received evolocumab or placebo in the FOURIER study regardless of whether the subjects enrolled in the OLE study.

The OLE safety analysis set (OLE study only) includes all subjects who received at least 1 dose of open-label evolocumab in the OLE study.

The OLE CANTAB analysis set (OLE study only) includes all subjects who enrolled in the EBBINGHAUS study and received at least 1 dose of open-label evolocumab in the OLE study.

10.1.3 Covariates and Subgroups

The planned covariates and subgroups include the following:

- age (< 65 years, ≥ 65 years)
- sex (male, female)
- race (white, non-white)

10.2 Sample Size Considerations

It is estimated approximately 5000 subjects who completed the FOURIER study will be enrolled. Based on a sample size of 5000 subjects, [Table 2](#) lists the width of 95% confidence intervals for a range of various underlying adverse event rates.

Table 2. Confidence Interval Width for Adverse Event Rates

Percent Underlying Adverse Event	Width of 95% Confidence Interval
0.01%	0.056%
0.05%	0.124%
0.10%	0.176%
1.00%	0.552%
2.00%	0.776%
3.00%	0.946%
4.00%	1.086%
5.00%	1.208%

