2.3 Rationale

This 5-year open-label extension (OLE) study is being conducted to provide additional safety data on the long-term administration of evolocumab. These additional safety data include the long-term effects of LDL-C < 40 mg/dL (< 1.03 mmol/L). A total of approximately 5000 subjects will be enrolled. Approximately 2000 subjects with 2 or

more years of study exposure in FOURIER will be enrolled in this OLE to provide safety and tolerability for subjects with 7 years of total study exposure (from the start of FOURIER to completion of the OLE). Assuming approximately 50% of these 2000 subjects were on evolocumab in FOURIER, approximately 1000 subjects will have 7 years of total evolocumab exposure. Additionally, subjects participating in the EBBINGHAUS study (Study 20130385; a substudy of FOURIER) will be provided the opportunity to enroll in the OLE so that additional long-term assessments of cognitive function will be performed, using the CANTAB.

The FOURIER OLE sites will be a subset of FOURIER sites. The FOURIER OLE study population will comprise the following subject groups:

- a) subjects who have at least 2 years of study exposure in FOURIER
- b) subjects from EBBINGHAUS, regardless of study exposure
- c) subjects who have less than 2 years of study exposure in FOURIER and did not participate in EBBINGHAUS

Enrollment of eligible subjects may be limited at the site level, to maintain a 1:1 ratio between subject groups “a” and “c” (ie, subjects who have \geq 2 years of study exposure in FOURIER and subjects who have less than 2 years of study exposure in FOURIER and did not participate in EBBINGHAUS) or to manage overall recruitment into the OLE.

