10.4 Planned Methods of Analysis

10.4.1 General Considerations

Statistical analyses in this open-label study will be descriptive in nature. No statistical inference or missing value imputation is planned. No formal hypotheses will be tested in this study. Subject disposition, demographics, and baseline characteristics will be summarized. Summary statistics for continuous variables will include the number of subjects, mean, median, standard deviation or standard error, minimum, and maximum. For categorical variables, the frequency and percentage will be given. Unless specified otherwise, the baseline value is defined as the subject's baseline value from the parent study (FOURIER/EBBINGHAUS).

For all endpoints, results will be summarized by the randomized treatment group from the FOURIER study and overall, unless specified otherwise.

The primary analysis of all primary, secondary, and exploratory endpoints will use data from the OLE study only. Additional analyses combining the data from the OLE study and FOURIER/EBBINGHAUS study will be performed as applicable.

All deaths and cardiovascular events of interest (MI, stroke, coronary revascularization, hospitalization for unstable angina, hospitalization for heart failure, and TIA) will be reviewed by an independent external CEC, using standardized definitions. The CEC is external to Amgen and primarily comprises both academic clinical physicians (to include cardiologists) and medical reviewers trained on the clinical trial protocol, the CEC charter, and CEC processes. The chairman of the CEC is responsible for overseeing the operations in conformance with the CEC charter and for supervising the flow of data between the sponsor/data management and the CEC. Committee members are qualified in the appropriate subspecialty and free of conflict of interest. The CEC reviews events according to pre-specified criteria defined in the CEC charter. The CEC will be blinded to the original randomized treatment group from the FOURIER study.

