9.1 General Considerations

Statistical analyses in this open-label study are descriptive in nature. No statistical inference is planned. No formal hypothesis will be tested in this study.

Subject disposition, demographics, and baseline characteristics, and exposure to IP will be summarized.

Summary statistics for continuous variables will include the number of subjects (n), mean, standard deviation (SD) or standard error (SE), median, the first (Q1) and third (Q3) quartiles, minimum, and maximum. For categorical variables, the frequency and percentage will be given. The baseline value is defined as the subject's baseline value

from the parent study as defined in [Section 5.2](#), unless specified otherwise. All analyses will be performed on the OLE safety analysis set.

For all endpoints, results will be summarized by the randomized treatment group from the parent study and overall, unless specified otherwise.

The analysis of all primary, secondary, and exploratory endpoints will use data from the OLE study only as well as the combined data from parent and OLE studies as applicable.

All deaths and cardiovascular events of interest (MI, coronary revascularization, hospitalization for unstable angina, heart failure, cerebrovascular events and coronary heart disease death) will be reviewed by an independent external CEC, using standardized definitions. The CEC is external to Amgen and primarily comprises both academic clinical physicians (to include cardiologists) and medical reviewers trained on the clinical trial protocol, the CEC charter, and CEC processes. The chairman of the CEC is responsible for overseeing the operations in conformance with the CEC charter and for supervising the flow of data between the sponsor/data management and the CEC. Committee members are qualified in the appropriate subspecialty and free of conflict of interest. The CEC reviews events according to pre-specified criteria defined in the CEC charter. The CEC will be blinded to the original randomized treatment group from the parent study.

There will be no imputation for missing data other than date imputation described in [Section 8.3.2](#).

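### Sample-size tables: at a 0.01% event rate the stated 95% CI width of 0.056% comes from an unnamed normal approximation with 0.5 expected events; small-count methods give widths 24% to 65% larger

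*Protocol*

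**What the plan says.** Protocol 10.2 (Table 2) and SAP 3.2 (Table 3-1) hold the same eight-row table. It is introduced with "Based on a sample size of 5000 subjects" and "lists the width of 95% confidence intervals for a range of various underlying adverse event rates". At a rate of 0.01% the stated width is 0.056%, at 0.05% it is 0.124%, and at 0.10% it is 0.176%. The remaining rows run from 1% (0.552%) to 5% (1.208%). Neither document says which interval was used.

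Three other places set the context:

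- Protocol 10.4.1: "No statistical inference or missing value imputation is planned".
- SAP 9.1: "No statistical inference is planned. No formal hypothesis will be tested in this study".
- Protocol 2.3 gives a separate, exposure-based reason for the enrolment target, namely that "approximately 1000 subjects will have 7 years of total evolocumab exposure".

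**The concern.** The primary objective is long-term safety, and the 0.01% row is the plan's statement about its rarest events. With 5000 subjects that rate means half an expected event, where a normal approximation to the binomial is not usable. Because the method is not named, a reader cannot see that the row rests on it.

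What is at stake is the planning statement itself. These tables are the only statistical precision statement offered for 5000 subjects, and the rare-event row makes the study look more informative than it can be.

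**Working it through.** **Inputs.** n = 5000, a 95% level, and the eight rates and widths, all from Protocol Table 2 and SAP Table 3-1. The two-sided z = 1.96 is inferred, because it reproduces the table.

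**Step 1: reproduce the table.** Wald width = 2 × 1.96 × √(p(1−p)/n). At p = 0.0001:

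- √(0.0001 × 0.9999 / 5000) = 0.00014141
- half-width = 1.96 × 0.00014141 = 0.0277%
- full width = 0.0554%

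Rounding the half-width to 0.028% and doubling gives the stated 0.056%. The same rule returns all eight stated values exactly, so the source of the table is clear and there is no slip in the calculation.

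**Step 2: what the 0.01% row implies.**

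- Expected events: 5000 × 0.0001 = 0.5.
- Implied lower limit: 0.01% − 0.028% = −0.018%. In the 0.05% row it is 0.05% − 0.062% = −0.012%.
- P(0 events) = 0.9999^5000 = 0.6065. P(1) = 0.3033, P(2) = 0.0758, P(3) = 0.0126.
- A Wald interval is 0 wide at 0 events, 0.078% at 1 event and 0.111% at 2 events. No whole-number count gives 0.056%.
- Wald coverage at this rate is 39.3%, chiefly because the zero-width interval at 0 events misses 0.01%. At 0.05% and 0.10% it is 91.7% and 87.0%.

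**Step 3: expected widths from small-count methods.** Expected width = Σ P(x) × width(x), with x distributed Binomial(5000, p). For Clopper-Pearson at 0.01% the first three terms are 0.6065 × 0.0738 + 0.3033 × 0.1109 + 0.0758 × 0.1396 = 0.0890. Counts of 3 or more add 0.0023, giving 0.0913%.

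All widths below are in percent.

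| Rate | Expected events | Stated | Wald, unrounded | Jeffreys | Mid-P | Clopper-Pearson | Wilson |
|---|---|---|---|---|---|---|---|
| 0.01 | 0.5 | 0.056 | 0.0554 | 0.0693 | 0.0776 | 0.0913 | 0.0923 |
| 0.05 | 2.5 | 0.124 | 0.1239 | 0.1267 | 0.1322 | 0.1467 | 0.1417 |
| 0.10 | 5 | 0.176 | 0.1752 | 0.1766 | 0.1808 | 0.1965 | 0.1876 |
| 1 | 50 | 0.552 | 0.5516 | 0.5518 | 0.5532 | 0.5718 | 0.5551 |
| 2 | 100 | 0.776 | 0.7761 | 0.7761 | 0.7771 | 0.7961 | 0.7783 |
| 3 | 150 | 0.946 | 0.9457 | 0.9456 | 0.9464 | 0.9655 | 0.9473 |
| 4 | 200 | 1.086 | 1.0863 | 1.0861 | 1.0868 | 1.1061 | 1.0875 |
| 5 | 250 | 1.208 | 1.2082 | 1.2079 | 1.2086 | 1.2279 | 1.2091 |

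Excess over the stated width, in the order Jeffreys, mid-P, Clopper-Pearson, Wilson:

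- 0.01%: 24%, 39%, 63%, 65% (0.013 to 0.036 percentage points)
- 0.05%: 2%, 7%, 18%, 14%
- 0.10%: 0.4%, 2.7%, 11.6%, 6.6%
- 1% and above: under 0.1%, at most 0.2%, 3.6% and 0.6%

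**Step 4: the zero-event case.** The upper limits with no events are 0.0502% (Jeffreys), 0.0599% (mid-P), 0.0738% (Clopper-Pearson, 1 − 0.025^(1/5000)) and 0.0768% (Wilson). With zero events the lower limit is 0, so these are also the widths. For the last three methods even this interval is wider than 0.056%.

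**The case against.** The strongest reply is that nothing has been miscalculated. The table gives a width for an assumed underlying rate, and putting that rate into a standard formula is an ordinary way to do so. Averaging the width over the event count is a different quantity, and the size of the gap depends on the method chosen. Agresti-Coull would be wider still (+94% truncated at zero, +116% untruncated), while the Wald interval truncated at zero would be narrower (0.0377%). Clopper-Pearson is conservative here, with 98.6% coverage at 0.01%, so not all of its 63% is missing precision. The 0.05% and 0.10% gaps are small under Jeffreys or mid-P. Finally, no planned output uses a Wald interval: adverse events are reported as subject incidence and exposure-adjusted rates, and no confidence interval is specified for them.

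Most of this stands. The formula was applied correctly, the exact excess depends on the method, the 0.05% and 0.10% rows are secondary, and no output is affected. It does not rescue the 0.01% row:

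- The table's own formula yields 0.056% for no possible count.
- All four small-count methods err in the same direction.
- Averaging is not what creates the gap. Putting the expected count of 0.5 into the formulas, as the table in effect does, gives 0.0732% (Jeffreys), 0.0934% (Clopper-Pearson) and 0.0947% (Wilson), each wider than the averaged figure.
- Jeffreys, the narrowest of the four, also covers 98.6% at this rate and is still 24% wider than stated.

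**Conclusion.** The concern holds, at minor severity. The 0.01% row is wrong as a statement of precision: 0.056% should be about 0.069% to 0.092%. The 0.05% row is too narrow by an amount that depends on the method, the 0.10% row at most slightly so, and the rows from 1% up are sound for planning.

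This rests on 5000 subjects, two-sided 95% intervals, a binomial event count, and the four methods shown. Measured against the unrounded Wald width of 0.0554%, the range would be about 25% to 67%.

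The consequence stops at the planning statement. The figure of 5000 is an enrolment estimate, not derived from a target width. The exposure rationale in Protocol 2.3 is separate, and no decision rule uses the table.

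**What to change.** Recompute all eight rows in Protocol Table 2 and SAP Table 3-1 with one method, and name it under each table. State that the entries are widths averaged over the binomial distribution of the event count. Either set below would serve. Both are in row order and rounded from unrounded values: 0.19647 and 0.96555 for Clopper-Pearson at 0.10% and 3%, and just under 1.0875 for Wilson at 4%.

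- Clopper-Pearson: 0.091%, 0.147%, 0.196%, 0.572%, 0.796%, 0.966%, 1.106%, 1.228%
- Wilson: 0.092%, 0.142%, 0.188%, 0.555%, 0.778%, 0.947%, 1.087%, 1.209%

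Add one sentence: if no events are seen in 5000 subjects, the exact (Clopper-Pearson) two-sided 95% upper limit is 0.074%. For the rarest events this tells the reader more than a width does.

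The cost is eight cells in each of two tables, a footnote and a sentence. The stated precision becomes less favourable for rare events and, if Clopper-Pearson is chosen, 1.6% to 3.6% wider from the 1% row up. Sample size, conduct and planned analyses do not change.

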10.3 Planned Analyses

10.3.1 Interim Analyses

Interim analyses will be performed to support safety data reporting and assessments of other listed endpoints. The study is not anticipated to stop early unless an unexpected safety signal is detected that is assessed by Amgen Safety to warrant study stop.

10.3.2 Primary Analysis

The primary analysis activities are commenced based on achieving the end of study milestone described in [Section 3.5.2](#).

10.4 Planned Methods of Analysis

10.4.1 General Considerations

Statistical analyses in this open-label study will be descriptive in nature. No statistical inference or missing value imputation is planned. No formal hypotheses will be tested in this study. Subject disposition, demographics, and baseline characteristics will be summarized. Summary statistics for continuous variables will include the number of subjects, mean, median, standard deviation or standard error, minimum, and maximum. For categorical variables, the frequency and percentage will be given. Unless specified otherwise, the baseline value is defined as the subject's baseline value from the parent study (FOURIER/EBBINGHAUS).

For all endpoints, results will be summarized by the randomized treatment group from the FOURIER study and overall, unless specified otherwise.

The primary analysis of all primary, secondary, and exploratory endpoints will use data from the OLE study only. Additional analyses combining the data from the OLE study and FOURIER/EBBINGHAUS study will be performed as applicable.

All deaths and cardiovascular events of interest (MI, stroke, coronary revascularization, hospitalization for unstable angina, hospitalization for heart failure, and TIA) will be reviewed by an independent external CEC, using standardized definitions. The CEC is external to Amgen and primarily comprises both academic clinical physicians (to include cardiologists) and medical reviewers trained on the clinical trial protocol, the CEC charter, and CEC processes. The chairman of the CEC is responsible for overseeing the operations in conformance with the CEC charter and for supervising the flow of data between the sponsor/data management and the CEC. Committee members are qualified in the appropriate subspecialty and free of conflict of interest. The CEC reviews events according to pre-specified criteria defined in the CEC charter. The CEC will be blinded to the original randomized treatment group from the FOURIER study.

10.4.2 Primary Endpoint

The current Medical Dictionary for Regulatory Activities version at the time of data lock will be used to code all adverse events **and disease related events** to a system organ class and preferred term. Exposure-adjusted subject incidence rates of all treatment-emergent adverse events, serious adverse events, fatal adverse events, adverse events leading to withdrawal from evolocumab, device-related adverse events, and disease related events will be tabulated for the overall OLE study period using the OLE safety analysis set. These events will also be presented by yearly subject exposure time intervals. **All adverse event summaries for the primary analysis of the primary endpoint will include all treatment-emergent events reported on the Event eCRF, including CEC reviewed events and disease related events.**

Adverse event data from the OLE study will also be combined with FOURIER study data as an additional analysis, and positively reviewed events will not be included in the adverse event analysis to remain consistent with FOURIER adverse event reporting. The analysis will be performed using the long-term safety analysis set.

10.4.3 Secondary Endpoints

Summary statistics of the secondary endpoints (percent change of LDL-C from baseline and achieving an LDL-C < 40 mg/dL) will be provided.

10.4.4 Exploratory Endpoints

Summary statistics for CANTAB assessments, including SWM strategy index of executive function, SWM between-errors score, PAL total errors adjusted, and RTI median 5-choice reaction time, will be provided based on the OLE CANTAB analysis set.

Summary statistics for percent change from baseline at each scheduled visit for each exploratory lipid parameter will be summarized.

Subject incidence of positively reviewed events (by an independent external CEC) will be summarized.

10.4.5 Additional Safety Analyses

Vital signs will be summarized using descriptive statistics at each scheduled visit.

Concomitant medications of interest and exposure to evolocumab will be summarized.

11. REGULATORY OBLIGATIONS

11.1 Informed Consent

An initial sample ICF is provided for the investigator to prepare the informed consent document to be used at his or her site. Updates to the template are to be communicated formally in writing from the Amgen clinical study manager to the investigator. The written informed consent document is to be prepared in the language(s) of the potential patient population.

Before a subject's participation in the clinical study, the investigator is responsible for obtaining written informed consent from the subject after adequate explanation of the aims, methods, anticipated benefits, and potential hazards of the study and before any protocol-specific screening procedures or any investigational product (evolocumab) is administered.

The acquisition of informed consent is to be documented in the subject's medical records, and the ICF is to be signed and personally dated by the subject and by the person who conducted the informed consent discussion. The original signed ICF is to be retained in accordance with institutional policy, and a copy of the signed consent form is to be provided to the subject.

If a potential subject is illiterate or visually impaired and does not have a legally acceptable representative, the investigator must provide an impartial witness to read the ICF to the subject and must allow for questions. Thereafter, both the subject and the witness must sign the ICF to attest that informed consent was freely given and understood.

